9.4.1 MISSING DATA

The analytic method for the primary endpoint will be generalized estimating equations (GEEs), which requires missing data to be missing completely at random for valid inference. We expect the rate of missing data to be small and anticipate GEE analysis to be appropriate. However, if the rate of missing data is significant, we will use linear mixed effect regression (LMER) as our primary analytic approach and GEEs as a secondary approach. A review of the data will be performed prior to database lock to establish overall rates of missingness for the primary endpoint and the SAP updated if needed to reflect any changes in planned analyses.

9.4.2 ANALYSIS OF THE PRIMARY ENDPOINT

We will use a model-based approach to analyze change in IMAGE-HN score from baseline to 6-month follow-up. Specifically, change in IMAGE-HN score will be modeled using a regression model with a factor for trial arm, covariates for the randomization stratification variable of site and free flap reconstruction, and pre-specified baseline covariates known to be prognostic for the primary endpoint including baseline IMAGE-HN score, gender, education, employment, tumor location, and adjuvant therapy.^{8,75} The selection of pre-specified baseline covariates known to be prognostic follows best practices for randomized clinical trials.¹⁰³ Additionally, adjusting for the baseline score in a change-score analysis is discussed at length by Frank Harrell and James Slaughter.¹⁰⁴ The GEE regression model was selected to account for the clustering of patients within psychologist (BRIGHT arm) or HN clinical staff member (AC arm). Our preferred model-based approach is a marginal model using GEEs because

subsequent inference best aligns with the trial's stated primary objective. Furthermore, GEEs are robust to variance misspecification. We will use GEEs with an identity link and an exchangeable working correlation structure. Final inference will be based on the robust sandwich estimator.

The primary analysis will use the 6-month IMAGE-HN evaluable set, which eliminates unit non-response, that is, patient data where the baseline or 6-month survey is not completed. However, the potential for survey item non-response exists. There are three types of item non-response to consider: (1) the item is missing at baseline and at follow-up; (2) the item is missing at baseline but not missing at follow-up; and (3) the item is not missing at baseline but is missing at follow-up. We expect the rate of item non-response at baseline to be 0% given training of study coordinators and our experience with the pilot study. In the event of item non-response at the 6-month follow-up, we adopt a conservative imputation approach to avoid inflation of treatment effect. Accordingly, we will impute the baseline value for the given item to reflect no change. As a sensitivity analysis, we will also impute the item's value from the most recent follow-up time prior to 6-months. Finally, depending on the extent of missing data, we may additionally perform sensitivity analyses using multiple imputation or treating survey total scores as interval censored.

To evaluate the inferential impact of our modeling choice (GEE) and cross-sectional (as opposed to longitudinal) data analyses, the following secondary analyses will be conducted using the 6-month IMAGE-HN evaluable set:

1. We will model change in IMAGE-HN score from baseline to 6-month follow-up using a LMER model with a factor for trial arm, the randomization stratification variables of site and free flap reconstruction, and pre-specified baseline covariates including baseline IMAGE-HN score, gender, education, employment, tumor location, and adjuvant therapy. Cluster-specific random effects will be included assuming an exchangeable correlation structure.
2. We will model change in IMAGE-HN score from baseline across all timepoints using GEEs and LMER models as described. Additional model terms for time (discrete), and trial arm-by-time interaction will be included.

All analyses described will be repeated using the per-protocol analysis set.

To evaluate the inferential impact of eliminating unit non-response in our primary analysis, the following additional sensitivity analyses will be performed using the FAS: (1) any trial participant missing the 6-month follow-up survey will be counted as having a 6-month total score equal to the baseline total score (no change from baseline); and (2) any trial participant missing the 6-month follow-up survey will be counted as having a 6-month total score equal to the maximum total score. Trial participants without a baseline survey will be excluded from these analyses.

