6.1.2.1 BRIGHT

BRIGHT will be delivered in one-on-one, face-to-face sessions between the study psychologist and participant using a standard of care video telemedicine platform. The BRIGHT intervention consists of 6 sessions of weekly, 60-minute, tablet-based, manualized individual video tele-CBT (see **Section 1.3, Schedule of Activities**). BRIGHT will be delivered by licensed clinical psychologists at each site with experience delivering manualized CBT and working with cancer survivors. The use of multiple psychologists to deliver BRIGHT will enhance rigor and external validity and minimize confounding between the experimental intervention and interventionist. The relevant parameters when considering the delivery of BRIGHT include the number, frequency, and duration of telemedicine sessions. Participants in the trial are permitted to interact with other participants after randomization, regardless of treatment allocation. Such encounters may occur in waiting rooms before or after clinic appointments given the single-site design of the trial. Such encounters may also occur in the virtual and social network space through patient support forums and online communities of HNC survivors.

6.1.2.2 AC

AC will be delivered in one-on-one, face-to-face sessions between the clinical provider and participant using a standard of care video telemedicine platform (see **Section 1.3, Schedule of Activities**). The relevant parameters when considering the delivery of AC include the number, frequency, and duration

of video telemedicine sessions to ensure that it is appropriately matched to BRIGHT. AC controls for professional attention (i.e., ensuring that findings are not driven by simply interacting with an empathic interventionist), common factors,²⁶ dose, and delivery method while not providing the active, behavior change mechanism in BRIGHT. A full dose of AC is not known. Participants in the trial are permitted to interact with other participants after randomization, regardless of treatment allocation. Such encounters may occur in waiting rooms before or after clinic appointments given the single-site design of the trial. Such encounters may also occur in the virtual and social network space through patient support forums and online communities of HNC survivors.

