9.2 SAMPLE SIZE DETERMINATION

The primary endpoint for the proposed RCT is the change in the IMAGE-HN score from baseline to 6-month follow-up. Our primary objective is to test the hypothesis that BRIGHT decreases HNC-related BID from baseline to 6-month follow-up (as measured by clinically significant reduction in the IMAGE-HN score) relative to AC. We target a mean difference in IMAGE-HN score reduction of 9 between BRIGHT and AC at 6 months. This targeted difference is (1) clinically important using widely accepted distribution-based methods of patient reported outcome measure interpretation⁸⁸ and (2) commensurate with clinically meaningful differences in BID among cancer survivors from other appropriately powered trials.^{14,41,100} In our pilot RCT, at 3-months post-intervention (a timepoint similar to 6 month follow-up), BRIGHT improved IMAGE-HN scores from baseline relative to AC (mean model-based difference in change in IMAGE-HN score = -17.1 [90% CI, -25.6 to -8.6] points; $P = 0.002$). The targeted clinically important difference in IMAGE-HN score reduction of 9 thus appears highly feasible. Determining the sample size for the proposed RCT requires adjusting for the clustering of trial participants within psychologist (BRIGHT arm) or HN clinical staff member (AC arm). We expect the number of clusters in each arm to be 9 with an average of 10 trial participants per cluster. We further estimate an intra-class correlation coefficient (ICC) = 0.05^{101,102} and standard deviation = 16 based on similar studies.^{41,100} Given these assumptions, a sample size of $N = 180$ ($n = 90/\text{arm}$) yields 83.7% power to detect the targeted 9-point average reduction in IMAGE-HN scores between the BRIGHT and AC arms with two-sided $\alpha = 0.05$ (PASS v 08.0.13, Inequality Tests for Two Means in a Cluster-Randomized Design module).

Targeting an attrition rate = 20%, we plan to enroll 226 HNC survivors with BID to achieve our target sample size of $N = 180$ evaluable patients for the modified intention-to-treat (ITT) analyses of the efficacy population. In our pilot RCT, 20% (11/54) of eligible patients who accrued to the RCT were not evaluable for the primary endpoint: $n = 7$ (13%) went off study per protocol due to the development of recurrent HNC or a second non-HNC malignancy; and $n = 3$ (7%) withdrew due to intercurrent physical demands. No patients were lost to follow-up.

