9.5 REGULATORY, ETHICAL, AND STUDY OVERSIGHT CONSIDERATIONS

9.5.1 SINGLE IRB COORDINATION

The study will be conducted under a single IRB study with MUSC IRB serving as the IRB of record. The MUSC IRB will initiate the reliance agreements with each relying institution, that each relying institution will be responsible for performing a local context review of the study to ensure that the protocol is appropriate and reasonable for their respective study populations. The structure and organization of the study team is shown is described below.

1. **Administrative Sites.** The overall administration of the study will occur at MUSC.
2. **Data Coordinating Sites.** MUSC will serve as the data coordinating site. Study documents will originate from MUSC and be disseminated to each site.
3. **Participating Sites.** In this multisite clinical trial comparing BRIGHT with AC, eligible patients with clinically significant HNC-related BID will be recruited from MUSC, HFH, and WUSM. Study procedures and assessments will be conducted at each site as described in the protocol.
4. **Separate Laboratory and Testing Centers.** There are no separate laboratory and testing centers.

5. Study Team Composition. The organization of the study team is shown in **Figure 8**. For the conduct of the trial, the structure of each study team is identical (site PI, psychologist, HNC Clinical staff, and program coordinator).

The study will be coordinated as an sIRB study with the following communication plan. Study documents will be maintained in a HIPAA-compliant and secure shared folder (MUSC Box) to which all non-MUSC study personnel will be given download access. Interactions among sites will be coordinated through site PIs via secure email, telephone call, or video telemedicine sessions (e.g., Microsoft Teams).

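### Section 9.4.2 rests the primary test on a robust sandwich estimator with only 18 therapist clusters and calls for no small-sample correction; in its standard form the nominal 5% test rejects about 9-12% of the time.

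*Protocol*

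**What the plan says.** Section 9.4.2 models change in IMAGE-HN at 6 months with a GEE (identity link, exchangeable working correlation) clustered on the psychologist in the BRIGHT arm or the clinical staff member in the AC arm. The covariates are site, free flap, baseline score, gender, education, employment, tumor location and adjuvant therapy. The choice of GEE is supported partly by the remark "Furthermore, GEEs are robust to variance misspecification", and the section closes the matter with "Final inference will be based on the robust sandwich estimator".

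Section 9.2 gives the cluster count: "We expect the number of clusters in each arm to be 9 with an average of 10 trial participants per cluster". It takes the power from the PASS "Inequality Tests for Two Means in a Cluster-Randomized Design module" and reports 83.7%.

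Two other places bear on the point. Section 9.4.2 plans a linear mixed model (LMER) with cluster random effects as a secondary check on the modelling choice. Section 9.4.1 says that, if missing data are significant, "we will use linear mixed effect regression (LMER) as our primary analytic approach and GEEs as a secondary approach"; it expects the rate of missing data to be small. Section 9.4.3 extends similar approaches to the secondary endpoints.

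**The concern.** The robustness that section 9.4.2 relies on is a property of the sandwich estimator when there are many independent clusters. Here there are 18, and arm is constant within therapist, so the treatment effect is estimated from between-cluster information only. With few clusters the residuals understate the true variation, most of all for a cluster-level covariate in a model with many mean parameters. The standard error is then too small on average and also variable, so a normal reference makes matters worse.

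At stake is the primary test of an efficacy trial: a false-positive rate near twice the stated 5%, a 95% confidence interval that is too narrow, and the same weakness in the secondary endpoints.

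**Working it through.** **Inputs from section 9.2:** 9 clusters per arm, 10 patients per cluster, ICC 0.05, SD 16, difference 9, two-sided alpha 0.05, stated power 83.7%.

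**Step 1: reproduce the stated power.**
- Design effect = 1 + (10 - 1) × 0.05 = 1.45.
- SE = 16 × √(2 × 1.45 / 90) = 2.872.
- Noncentrality = 9 / 2.872 = 3.13.
- Noncentral t, 18 - 2 = 16 df: 83.67%, which matches.
- Normal reference: 87.97%. t on 178 df: 87.6%. Neither matches.

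**Step 2: count the mean parameters.** Category counts follow the subgroup definitions in section 9.4.6: intercept 1, arm 1, site 2, free flap 1, baseline score 1, gender 1, education 1, employment 2, tumor location 1, adjuvant therapy 1. The total is 12, against 18 clusters.

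**Step 3: simulate under no effect.** Exchangeable identity-link GEE, Gaussian outcome, 90 patients per arm, 6,000 to 16,000 runs per row, df = clusters - 2. The documents do not give the covariate distributions, the number of therapists per site or the spread of cluster sizes. These were assumed, with three therapists per site per arm unless stated, and varied. Cells are type I error in %; CV is the coefficient of variation of cluster size. KC = Kauermann-Carroll, MD = Mancl-DeRouen.

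| Scenario | Uncorrected, normal | Uncorrected, t | KC, t | MD, normal |
|---|---|---|---|---|
| 18 equal clusters, full model | 11.3 | 8.8 | 5.3 | 3.8 |
| same, covariate R² 0.2 | 11.0 | 8.8 | 5.3 | 3.8 |
| same, arm only | 8.7 | 6.8 | 5.3 | 5.8 |
| same, therapists not nested in site | 9.3 | 7.1 | 5.1 | 4.9 |
| same, ICC 0 | 12.0 | 9.9 | 6.1 | 4.4 |
| same, ICC 0.10 | 11.0 | 8.3 | 4.9 | 3.6 |
| 18 clusters, CV 0.28 | 13.3 | 10.8 | 6.5 | 4.5 |
| 18 clusters, CV 0.36 | 14.0 | 11.7 | 7.1 | 4.9 |
| 18 clusters, CV 0.47 | 14.9 | 12.5 | 7.2 | 4.8 |
| 12 equal clusters | 15.9 | 11.8 | 6.1 | 4.2 |
| 6 equal clusters | 40.2 | 27.4 | 13.0 | 7.9 |

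Monte Carlo 95% error is about 0.5 point in the first row and at most 1.3 points elsewhere. Further simulations of the 18-equal-cluster full model, with separately chosen assumptions, gave 10.8% to 12.3% (uncorrected, normal) and 8.3% to 9.7% (uncorrected, t). Arm-only runs gave 8.3% to 9.1%.

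**Step 4: why a t reference alone is not enough.** In the first row the mean estimated SE divided by the true SE is 0.850 (uncorrected), 0.982 (KC) and 1.137 (MD). With the uncorrected SE, the normal cut-off sits at 1.960 × 0.850 = 1.67 true standard errors and the t(16) cut-off at 2.120 × 0.850 = 1.80. Both are short of 1.96, even before the variability of the SE is counted.

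**Step 5: the mixed model on the same data.** With 18 equal clusters and the full model, the LMER rejects 6.0% with a normal reference and 4.1% with Kenward-Roger df.

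**The case against.** The strongest reply is that the protocol never says uncorrected and never says normal reference. Section 9.4 leaves detailed methods to an SAP that was not available here, and a variance correction is the sort of detail an SAP can supply. That stands as a limit: the error rates above are conditional. It does not dispose of the point. The protocol itself fixes the inferential basis and defends it by a property that does not hold well at the cluster count it plans.

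Three stronger readings are tempting and are not supported:
- *That sections 9.2 and 9.4.2 contradict each other.* Section 9.2 implies t on 16 df; section 9.4.2 names no reference distribution. Silence is not a conflict. The most that can be said is that the allowance is not carried over.
- *That the test has an 11% error rate.* The figure depends on covariate distributions and on nesting of therapists in site, which the documents do not give. A range is the honest statement.
- *That there will be only six clusters*, because section 9.5.1 lists "the structure of each study team is identical (site PI, psychologist, HNC Clinical staff, and program coordinator") for each site. That is a list of roles, not a headcount. Section 9.2 states nine clusters per arm, and section 6.1.2.1 refers to psychologists at each site in the plural.

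The LMER is a real safeguard, since disagreement with the GEE could expose a narrow standard error. But it is secondary when missing data are few, which is what the protocol expects, and no df method is named for it.

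**Conclusion.** The point holds in conditional form and should be fixed before outcome data are analysed. If the sandwich is used in its standard uncorrected form with a normal reference, the nominal 5% primary test rejects about 9-12% of the time with 18 equal clusters. The result changes little across ICC 0 to 0.10 or with covariate R² of 0.2. The 13-15% seen with unequal clusters depends on assumed size patterns, and the conclusion does not rest on it. The simulations cover a continuous Gaussian outcome; the protocol's own inputs fix the cluster count, cluster size, ICC and SD.

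**What to change.** Keep the GEE and replace the closing sentence on inference in section 9.4.2 with one fixed rule:

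> Final inference will use a small-sample bias-corrected sandwich estimator (Kauermann-Carroll) with a t reference on (number of therapist clusters - 2) degrees of freedom.

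Simulated type I error is about 5-6% with 18 equal clusters and about 6-7% with unequal ones. Power for 9 points is 82.6% at covariate R² 0, near the stated 83.7%, and 90.2% at R² 0.2.

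If strict control under unequal clusters is preferred, name Mancl-DeRouen with a normal reference instead (about 4-5% in the full model). The power in section 9.2 must then be restated, with the method and assumed R². At R² 0 it is 79.0% with equal clusters, and 77.2% and 75.3% at assumed CVs of about 0.29 and 0.49; at R² 0.2 with equal clusters it is 87.3%. Choose one estimator in advance; a switch on cluster-size spread is not needed.

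Apply the same rule to the secondary endpoints analysed by GEE, and name Kenward-Roger df for the LMER. If far fewer than 12 clusters are realised, neither correction is adequate (13.0% and 7.9% with six), and the method must be re-examined before database lock.

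The cost is wording, with no new data and no change in N; both corrections can be run in SAS or R. The interval widens relative to the uncorrected one: by (2.120 × 0.982) / (1.960 × 0.850) = 1.25, or 25%, for Kauermann-Carroll with t(16), and by 1.137 / 0.850 = 1.34, or 34%, for Mancl-DeRouen with a normal reference.

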9.3 POPULATIONS FOR ANALYSES

The **safety analysis set** (SAS) is composed of all patients enrolled who receive any part of either the BRIGHT or AC intervention. The SAS will be used to conduct all safety analyses. Patients will be analyzed based on the intervention received regardless of the assignment at randomization.

The **6-month IMAGE-HN evaluable set** is composed of all patients enrolled in the trial who have completed the baseline and 6-month follow-up IMAGE-HN survey instrument. Analysis will be performed based on assignment at randomization regardless of the intervention received (modified intent to treat). This analysis set will be used for analysis of the primary endpoint.

Analysis sets for secondary endpoints specific to PROMs at a given follow-up timepoint will be defined as the set of trial participants who have completed both the baseline and the follow-up survey at the specified timepoint. Analysis will be performed based on assignment at randomization regardless of the

intervention received (modified intent to treat). These analysis sets will be used for analysis of the secondary endpoints (**Table 5**).

The **full analysis set (FAS)** is the set of all trial participants who enroll and are eligible for the study. Patients who enroll but subsequently drop out prior to receiving any of the assigned intervention will be replaced. This analysis set will be used for secondary analyses of both the primary endpoint and secondary endpoints.

Per protocol set is composed of all patients enrolled in the trial who have completed 6-weeks of the BRIGHT/AC interventions as described in the protocol. This analysis set will be used for secondary analyses of both the primary endpoint and secondary endpoints.

Details about the analytic plan for each population are described in detail in **Section 9.4**.

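### The mixed-model fallback for missing data, read as written, runs on 6-month completers only, so the switch from GEE changes almost nothing; the expectation of little missing data also needs reconciling with the planned 20% loss

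*Protocol*

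**What the plan says.** Section 9.4.1 names GEE as the method for the primary endpoint and notes that it needs data missing completely at random. It continues: "We expect the rate of missing data to be small and anticipate GEE analysis to be appropriate". The contingency is: "if the rate of missing data is significant, we will use linear mixed effect regression (LMER) as our primary analytic approach", with GEE then secondary. The overall missingness rate for the primary endpoint is to be reviewed before database lock. No analysis set is given for the fallback.

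The set is given elsewhere. Section 9.3 defines the 6-month evaluable set as "patients enrolled in the trial who have completed the baseline and 6-month follow-up IMAGE-HN survey instrument" and assigns it to the primary endpoint, with no exception for a change of model. Section 9.4.2 repeats this: "The primary analysis will use the 6-month IMAGE-HN evaluable set, which eliminates unit non-response". It then describes two sets of LMER analyses, one of the 6-month change and one across all timepoints with an arm-by-time interaction, under the statement that "the following secondary analyses will be conducted using the 6-month IMAGE-HN evaluable set". It adds: "All analyses described will be repeated using the per-protocol analysis set".

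Section 9.2 states: "Targeting an attrition rate = 20%, we plan to enroll 226 HNC survivors with BID", to end with 180 evaluable. Of the pilot it says: "20% (11/54) of eligible patients who accrued to the RCT were not evaluable for the primary endpoint".

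**The concern.** The only statistical reason in 9.4.1 for leaving GEE is its missing-data requirement. A likelihood-based mixed model can relax that requirement to missing at random, but only if patients with incomplete follow-up are in the model, so that their 2- and 3-month scores inform the 6-month contrast. A model fitted to 6-month completers has no missing 6-month outcome to handle. It conditions on completion just as the GEE does.

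Reading 9.4.1 as being about unanswered items does not help. Section 9.4.2 already fills a missing 6-month item with its baseline value, so no missing total would be left for the LMER to deal with.

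At stake is whether the one safeguard attached to the primary analysis works in the situation for which it was written. That situation is close to the planned one: a fifth of enrolled patients are expected to be non-evaluable, while 9.4.1 justifies GEE by expecting little missing data. Some of the loss could follow engagement with the assigned arm, because 6.4 makes attendance a condition of staying active and 7.2 allows removal for non-compliance.

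**Working it through.** **1. The plan's own figures.** Inputs from 9.2: difference 9, SD 16, ICC 0.05, 9 clusters of 10 per arm, two-sided alpha 0.05.
- Design effect = 1 + (10 − 1) × 0.05 = 1.45.
- SE = 16 × √(2 × 1.45 / 90) = 2.87.
- Power from the noncentral t with 2 × 9 − 2 = 16 df = 83.7%, as stated.
- Enrolment: 90 / 0.8 = 112.5, rounded up to 113 per arm, gives 226, as stated.

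**2. Planned missingness.** (226 − 180) / 226 = 46/226 = 20.4%. Pilot: 11/54 = 20.4%. Pilot withdrawals alone: 3/54 = 5.6%.

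**3. Who is in each analysis of the primary endpoint.**

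| Analysis | Set | Uses 2- and 3-month scores of patients with no 6-month survey? |
|---|---|---|
| Primary GEE | 6-month completers | No |
| LMER, 6-month change | 6-month completers | No |
| GEE and LMER, all timepoints | 6-month completers | No |
| Repeats in the per-protocol set | Completed 6 weeks of intervention | Possible in the all-timepoint models, but selected on adherence |
| Two FAS sensitivity analyses | Eligible enrolled patients with a baseline | No; no-change or maximum-score value inserted |
| Multiple imputation | Optional | Not committed |

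**4. Bias of a completer analysis.** These are assumptions, not protocol figures, except the 9-point difference and SD 16: true mean changes −14 and −5; 20% lost in each arm; in one arm a stated share of patients is lost with log-odds rising by the slope per SD of 3-month score, and other loss is random; correlation between 3 and 6 months 0.4 to 0.7. There were 2,000,000 simulated patients per arm. Bias, in either direction:

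| Response-related share of that arm | Slope 0.5 | Slope 1.1 |
|---|---|---|
| 5.6% (pilot withdrawals) | 0.2 to 0.3 | 0.3 to 0.6 |
| 10% | 0.3 to 0.6 | 0.6 to 1.1 |
| 20% (all loss) | 0.6 to 1.1 | 1.2 to 2.1 |

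At correlation 0.6 with the full 20%, the estimate is −8.07 (slope 0.5) or −7.20 (slope 1.1) when AC has the response-related loss, and −9.91 or −10.79 when BRIGHT has it. The bias of −7.20 is 9 − 7.20 = 1.8.

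If both arms have the same slope and the same 20% loss, the bias is about zero. If instead one common rule acts on the absolute 3-month change, the better-improving arm loses fewer patients and the rates differ. The estimate is then about −8.8 (slope 0.5) or −8.3 (slope 1.1), taking 3-month means equal to the 6-month means and correlation 0.6.

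**5. Power if the effect is diluted** (SE 2.87, 16 df): 8.8 gives 82.0%, 8.5 gives 79.3%, 7.9 gives 73.3%, 7.2 gives 65.3%. If the bias runs the other way, the effect is overstated instead.

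**6. What the switch does.** In simulated trials (90 per slope, 113 patients per arm, 9 clusters per arm, ICC 0.05, no covariates, response-related loss in AC), GEE and the 6-month LMER on the same completers differed by 0.07 points on average, and GEE and the all-timepoint completer LMER by 0.10.

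**7. What including everyone does.** For a longitudinal likelihood analysis of all randomised patients (correlation 0.6, 20% share, AC case), the estimate depends on how many dropouts lack a 3-month score:

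| Dropouts lacking a 3-month score | Slope 0.5 | Slope 1.1 |
|---|---|---|
| None | −8.99 | −8.99 |
| Half | −8.58 | −8.19 |
| All | −8.07 | −7.20 |

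**The case against.** **The SAP can settle the set.** Section 9.4 defers detail to a SAP, and 9.4.1 allows it to be updated after the missingness review. If the protocol were silent, that would dispose of the point. But 9.3 and 9.4.2 already assign the completer set, and a SAP that follows them inherits it. Changing the set after missingness has been seen would be a data-driven choice.

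**The defect is inferred.** This is partly right. No sentence says that the LMER stays on completers once it becomes primary, and the protocol never mentions missing at random. Both are inferences, though they are the natural reading of the text.

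**The 20% is attrition, mostly benign.** Seven of the 11 pilot exits were recurrence or second malignancy, one was an erroneous enrolment, and nobody was lost to follow-up. Section 5.5.5 expects fewer cancer-related exits. Section 7.1 keeps patients who stop the intervention in follow-up. All of this stands and points to the lower end of the bias range. Still, 20% remains the planning figure, and 9.2 describes the pilot loss as non-evaluable for the primary endpoint.

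**Dropouts are not ignored.** A reader might infer that no analysis retains them. That is not so: two FAS sensitivity analyses are committed to test the effect of removing unit non-response, and the mediation models in 9.4.3 use maximum likelihood for missing data. Neither, however, gives a likelihood-based 6-month efficacy estimate that uses dropouts' earlier scores.

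**Little may be recovered.** All 44 pilot patients who completed the intervention gave 1- and 3-month post-intervention data (2.2.9), which suggests that those who leave may do so early and lack post-baseline scores. This is a real limit on the remedy.

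**Conclusion.** The point holds as a rule that does not do its job. As written, the fallback would fit the LMER to the same patients as the GEE and leave the estimate practically unchanged. The expectation of small missingness also needs reconciling with 46/226 planned as non-evaluable.

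A reader might go further and infer that the primary result will be biased, or biased in favour of BRIGHT. The documents do not support that. Bias needs loss that is related to response and differs between arms in mechanism or rate, and it can go either way. Anchored to the pilot withdrawals with a moderate slope it is about 0.2 to 0.3 points, roughly a tenth of the 2.87 SE. It reaches about 1 point if all 20% is response-related in one arm, and 1.8 with the steep slope at correlation 0.6. It is near zero if loss is equally response-related at equal rates in both arms, but a common rule on absolute 3-month change still dilutes −9 to about −8.8 or −8.3. These sizes rest on the assumed slopes and correlations. This should be fixed because the remedy is cheap, with medium confidence in how much it matters.

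**What to change.** State in 9.3 and 9.4.1 that the fallback is the all-timepoint, arm-by-time LMER already described in 9.4.2, fitted by assigned arm to all randomised patients with a baseline and any post-baseline IMAGE-HN score, with patient and interventionist effects, and with the 6-month contrast as the reported result. Run it whatever the observed missingness rate, alongside the completer GEE, so that nothing turns on a judgement of what counts as significant. Reword 9.4.1 so that its expectation agrees with the 20% in 9.2, or say which kind of missingness it means.

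The cost is wording in 9.3, 9.4.1 and 9.4.2 and some programming, with no new data and no change in sample size. The price is a longer model, a missing-at-random assumption, and little recovery for dropouts with no post-baseline score. For those patients the committed FAS sensitivity analyses remain. Multiple imputation on all randomised patients would be a useful optional supplement.
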